#### 3.2. Secondary Endpoints

The secondary endpoints for the study are:

- Comparison of primary and secondary efficacy parameters between doses
- Incidence of adverse events (AEs), serious adverse events (SAEs), and changes in laboratory test results
- Bone marrow improvement:
  - Bone marrow response rate at weeks 12, 24, and 36
  - Duration of bone marrow response
- Hemoglobin improvement

Baseline Status	Categories of Hemoglobin Improvement
Subjects who are transfusion dependent ( $\geq 2$ units PRBC every 4 weeks for 12 weeks prior to or after C1D1), regardless of baseline hemoglobin level	Percent of subjects with Red cell transfusion independence (no transfusions for $\geq 12$ consecutive weeks)  OR  50% reduction in RBC transfusions for $\geq 12$ consecutive weeks
Subjects with baseline hemoglobin $< 100$ g/L AND Not transfusion dependent	Percent of subjects with $\geq 10$ g/L and $\geq 20$ g/L increase in hemoglobin for $\geq 12$ consecutive weeks without transfusions

- Platelet improvement

Baseline Status	Categories of Platelet Improvement
Subjects who are transfusion dependent ( $\geq 2$ platelet transfusions in any 12 weeks prior to or after C1D1), regardless of baseline platelet level	Percent of subjects with: Platelet transfusion independence (no transfusions for $\geq 12$ consecutive weeks)  OR

Platelet transfusion = either 1 unit apheresed (single donor) platelets or 4-8 units pooled random donor platelets	50% reduction in platelets transfusions for $\geq$ 12 consecutive weeks
Subjects with $25 < \text{baseline platelets} < 50 \times 10^9/\text{L}$  AND Not platelet transfusion dependent	Percent of subjects with: Doubling of baseline platelet count for $\geq$ 12 consecutive weeks without platelet transfusions  OR  Platelet count $> 50 \times 10^9/\text{L}$ for $\geq$ 12 consecutive weeks without platelet transfusions,
Subjects with baseline platelet count $< 25 \times 10^9/\text{L}$  AND Not platelet transfusion dependent	Percent of subjects with: Doubling of baseline platelet count for $\geq$ 12 consecutive weeks without platelet transfusions  OR  Platelet count $> 25 \times 10^9/\text{L}$ for $\geq$ 12 consecutive weeks without platelet transfusions

- Hematologic improvement

Baseline Status	Categories of Hematologic Improvement

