### **7.11.1 Bone Marrow Biopsy**

Bone marrow biopsy will be performed at screening, Cycle 4, Day 1, Cycle 7, Day 1, and Cycle 9, Day 29. Analysis will include confirmation of diagnosis and assessments of reticulin stain and trichrome stain. Slides will be sent to a central committee of hematopathologists who will be

blinded to subject, treatment, and collection time for centralized grading of fibrosis. A charter will be established for the central committee. Quantification of marrow fibrosis will be performed in a blinded fashion by computer assisted image analysis. Unstained slides will be collected for analysis of disease and mechanism related changes.

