**Bone Marrow Biopsies:**

An optional bone marrow biopsy will be performed every 12 weeks.

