2.2.2 Secondary Efficacy Endpoints

The secondary efficacy endpoints are as follows for:

Stage 1:

- Bone Marrow MF grade shifts relative to baseline over time
- Modified Myeloproliferative Neoplasm-Symptom Assessment Form Total Symptom Score (MPN-SAF TSS) changes from baseline over time

Stage 2:

- Bone Marrow improvement:
 - Bone marrow (BM) response rate (MF Grade) at each visit (reduction of 1 grade versus baseline)
 - Duration of BM response defined for responding subjects as time from first decrease from baseline of one grade to time of return to baseline levels. If no return to baseline levels or worse than baseline then duration will be censored at the last BM assessment.
- Hemoglobin improvement (number and percentage of subjects):
 - For red blood cell transfusion dependent subjects at baseline (at least 2 units every 4 weeks for 12 weeks prior to Cycle [C]1Day [D]1), improvement is defined as either:
 - 1) absence of any packed red blood cells (PRBC) transfusion during any consecutive 12 weeks interval with hemoglobin level of ≥80g/L

OR

- 2) at least a 50% reduction in PRBC transfusions for 12 consecutive weeks with hemoglobin level of ≥80g/L
- For red blood cell transfusion independent subjects improvement is defined as:
 - ≥10 g/L increase in hemoglobin level for 12 consecutive weeks without transfusions
- Platelet improvement (number and percentage of subjects)

- For transfusion dependent subjects at baseline, improvement is defined as either:
- 1) becoming transfusion independent for 12 consecutive weeks

OR

- 2) reduction in transfusions need ≥50% from baseline for 12 consecutive weeks
- For transfusion independent subjects with baseline platelet count below 100^9/L, improvement is defined as:
 - ≥50% increase in the number of platelet for 12 consecutive weeks or normalization of platelet count (above lower limit normal)
- Symptom improvement:

Percent of subjects with 50% reduction in MPN-SAF TSS from baseline over time(Tefferi 2013)

• Percent of subjects with complete response, partial response, clinical improvement, stable disease and progressive disease according to IWG-MRT criteria.

2.2.3 Exploratory Efficacy Endpoints

The exploratory efficacy endpoints are as follows for:

Stage 1:

- Bone marrow biopsy results for:
 - Myeloblasts (%), at each time point and change from baseline
 - Cellularity (%), at each time point and change from baseline
 - Collagen and reticulin grade shifts relative to baseline over time

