- Myeloblasts and cellularity will be presented at baseline, Weeks 12 and 24 as well as change from baseline
- Collagen grade shifts relative to baseline at Weeks 12 and 24.

The modified MPN-SAF TSS will be presented descriptively at baseline and at the beginning of each cycle (Cycle 2 onward). In addition, the number of subjects with \geq 25% and \geq 50% reduction relative to baseline at the beginning of each cycle (Cycle 2 onward) will be presented.

Stage 2:

Duration of effect of the three doses on reduction in bone marrow fibrosis:

- To assess the duration of effect of the three doses on bone marrow improvement a
 Kaplan-Meier plot will be provided. Duration of BM improvement will be defined for
 responding subjects as time from first decrease from baseline of one grade to time of
 return to baseline levels. If no return to baseline levels then duration will be
 censored at the last BM assessment
- Effect and duration of effect of the three doses on disease related anemia, thrombocytopenia, and constitutional symptoms: For patients with improvement, the duration of improvement is defined as the number of weeks of improvement from the first12 weeks of improvement period.

IWG-MRT response will be summarized by treatment group at each visit by percent of subjects with complete response, partial response, clinical improvement, stable disease and progressive disease according to IWG-MRT criteria.

4.4.3 Exploratory Efficacy Endpoints

The exploratory endpoints will be summarized using tables, listings and graphs as appropriate.

4.4.4 Sensitivity Analyses

For Stage 2, a non-stratified analysis of BMRR will be computing as a sensitivity analysis.

4.4.5 **Subgroup Analyses**

Stage 1:

• Primary endpoint results will be presented by risks groups (intermediate-1, intermediate-2, or high risk subjects).

Stage 2:

- Primary endpoint results will be presented:
 - by risks groups (intermediate-1, intermediate-2, or high risk subjects)
 - for each strata separately (baseline anemia alone, baseline thrombocytopenia alone, baseline anemia and thrombocytopenia)
 - by transfusion status at baseline with transfusion dependency defined as: ≥ 2
 units PRBC every 4 weeks for 12 weeks prior to or after C1D1
 - by PTX-2 level at baseline classify by High/Low category (median as the cutoff)

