4.8 OLE STUDY ANALYSES

The OLE analyses will be performed separately for the OLE Stage 1 and Stage 2.

The listings will include the treatment regimen the patient received during the main stage and during the OLE.

For Stage 1, OLE begins with the first infusion of Cycle 7. As with the main study, cycles are 28 days in length. The "OLE Baseline" consists of assessments at the end of Cycle 6 / beginning of Cycle 7 (pre-dose).

For Stage 2, OLE begins with the first infusion of Cycle 10. As with the main study, cycles are 28 days in length. The "OLE Baseline" consists of assessments at the end of Cycle 9 / beginning of Cycle 10 (pre-dose).

The synopses for the OLE are in Appendix 2 and Appendix 4.

The primary and secondary endpoints for both stages, will be also produced on the OLE population when applicable. The OLE tables will be classified as per the original dose

received on the main stage and overall. For subjects who change doses, improvement will be analyzed.

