APPENDIX J: Stage 2 Extension Study

Sponsor:

Promedior, Inc

Name of Finished Product:

Recombinant human Pentraxin-2; PRM-151

Study Title:

A Phase 2, Prospective Study Of PRM-151 In Subjects With Primary Myelofibrosis (PMF), Post-Polycythemia Vera MF (post-PV MF), Or Post-Essential Thrombocythemia MF (post-ET MF)

Study Number:

PRM-151G-101

Study Phase: Phase 2

Investigational Product; Dose; and Mode of Administration:

PRM-151 10 mg/kg intravenous

Comparator; **Dose**; and **Mode** of Administration:

Not applicable

Primary Objective(s):

To provide subjects in the parent study an opportunity to remain on treatment and to allow all subjects to switch to an open label extension utilizing the 10mg/kg dose after completing 9 cycles of the originally assigned treatment.

Secondary Objective(s):

- To collect long term safety data of subjects receiving PRM-151
- To collect additional efficacy data on duration of response beyond 36 weeks of treatment
- To collect efficacy data on the change of PRM-151 dose level in subjects not achieving a response

Study Design:

This is an open-label extension of study PRM151G-101 to provide continued access to subjects in the parent study. All subjects completing 9 cycles of the originally assigned treatment may switch to an open label extension and receive PRM-151 10mg/kg every 4 weeks. The first cycle of the open label phase contains a loading dose of 10mg/kg on days 1,3 and 5. This will allow for subjects from all three dosing cohorts to receive a loading dose of 10mg/kg while maintaining the blind. Additionally, subjects who have entered the open label extension study prior to the approval of this amendment may receive a loading dose (10 mg/kg on days 1, 3, and 5), to be administered on their next scheduled cycle after approval of this protocol amendment. This will allow for these subjects to receive any potential pharmacologic benefit of the loading dose.

Study Duration:

Subjects may continue with PRM-151 dosing in the absence of disease progression or toxicity warranting discontinuation of therapy until drug is made available in another way. Cycle numbers will continue from the parent protocol, with Cycle 9 Day 29 of the parent protocol becoming Cycle 10 Day 1 of the extension study.

Response Assessments:

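### Stage 2 duration of marrow response counts only return to baseline grade as an event, so responders who die are censored and the Kaplan-Meier curve has no clear estimand once competing events occur

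*SAP*

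**What the plan says.** Protocol section 3.2 lists "Duration of bone marrow response" as a secondary endpoint and gives neither an event nor a censoring rule. The SAP supplies both. Section 2.2.2 (Stage 2) measures duration in responders as "time from first decrease from baseline of one grade to time of return to baseline levels" and adds: "If no return to baseline levels or worse than baseline then duration will be censored at the last BM assessment". Section 4.4.2 repeats the rule without the words about grades worse than baseline, and says that a "Kaplan-Meier plot will be provided".

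Neither section mentions death, leukemic transformation, progression, transplant or new anti-myelofibrosis therapy. The only sensitivity analysis listed (SAP 4.4.4) is a non-stratified analysis of the primary response rate.

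Two further provisions determine how much this matters:
- **Main-stage biopsies** (protocol 7.11.1): "Bone marrow biopsy will be performed at screening, Cycle 4, Day 1, Cycle 7, Day 1, and Cycle 9, Day 29", that is, weeks 12, 24 and 36 after baseline. The end-of-study visit (protocol 8.6) has no biopsy.
- **Extension** (protocol Appendix J): "An optional bone marrow biopsy will be performed every 12 weeks". One of its secondary objectives is "To collect additional efficacy data on duration of response beyond 36 weeks of treatment", and SAP 4.8 states: "The primary and secondary endpoints for both stages, will be also produced on the OLE population when applicable".

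**The concern.** Duration of effect on marrow fibrosis is a stated secondary objective, and duration past week 36 is an objective of the extension. By plain reading, a responder who dies with the last biopsy still improved contributes a censored time. Kaplan-Meier then treats that subject as if he or she would have gone on to face the same risk of histological loss as those still under observation. After death no later histological loss can be seen, so this is a competing event and not ordinary loss to follow-up.

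Elsewhere the SAP links such events to failure. Time to treatment failure (2.2.3) counts death and progression, and in Stage 1 (2.2.1) a marrow improvement outside the IWG-MRT response categories counted only together with at least stable disease. The Stage 2 duration rule does neither. A reader could take the height of the curve as the share of responders who are alive and still improved, which it does not estimate.

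**Working it through.** **Is there a figure to reproduce?** No. Neither document states a duration, a rate of histological loss, or a rate of death or progression among responders. The calculation below is illustrative.

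**Number of responders.** Protocol 10.1 assumes a 46% response in the 10 mg/kg arm and at least that in the 3 mg/kg arm. With the planned 24 per arm, 0.46 x 24 = 11.0. With 84/3 = 28 enrolled per arm, 0.46 x 28 = 12.9. So there are about 11-13 responders per higher-dose arm.

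**Longest observable duration in the main stage.** First response at week 12 and last biopsy at week 36 give 24 weeks. A response first seen at week 36 contributes 0 weeks.

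**Assumed rates (not in the documents).** Histological loss is 20% per 24 weeks. Competing events are 5%, 10% or 15% per 36 weeks. The 15% borrows the protocol's all-cause discontinuation allowance as a scale only. With constant hazards per week:
- l1 = -ln(0.80)/24 = 0.00930
- l2 = -ln(0.95)/36 = 0.00142; -ln(0.90)/36 = 0.00293; -ln(0.85)/36 = 0.00451

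**Formulas.**
- Curve under the SAP rule: KM(t) = exp(-l1 t)
- Alive, event-free and in response: C(t) = exp(-(l1 + l2) t)
- Cumulative incidence of histological loss: CIF(t) = [l1/(l1 + l2)] x [1 - C(t)]

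**Results.**

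| Competing events per 36 weeks | Weeks from response | KM | C | KM - C (points) | 1 - KM | CIF |
|---|---|---|---|---|---|---|
| 5% | 24 | 80.0% | 77.3% | 2.7 | 20.0% | 19.7% |
| 10% | 24 | 80.0% | 74.6% | 5.4 | 20.0% | 19.3% |
| 15% | 24 | 80.0% | 71.8% | 8.2 | 20.0% | 19.0% |
| 5% | 96 | 41.0% | 35.7% | 5.2 | 59.0% | 55.7% |
| 10% | 96 | 41.0% | 30.9% | 10.0 | 59.0% | 52.5% |
| 15% | 96 | 41.0% | 26.6% | 14.4 | 59.0% | 49.4% |

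Both errors are present at once. The curve is too high for C, and its complement is too high for the cumulative incidence: by 1 point or less at 24 weeks and by about 3-10 points at 96 weeks.

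**Dependence on the assumptions.** At 12-weekly biopsies, let q be the probability of histological loss among those biopsied and d the probability of a competing event that ends biopsies. Then KM is the product of (1 - q), and the event-free proportion in response is the product of (1 - q)(1 - d). The ratio is 1/product(1 - d), whether or not the two risks are correlated, provided that biopsies stop only because of those events. With q = 20% and d = 1 - 0.85^(1/3) = 5.3%, the 24-week values are 0.80^2 = 64.0% against (0.80 x 0.947)^2 = 57.4%, a gap of 6.6 points. Over q = 10-30% and d = 2-15% per 12 weeks, the gap at 24 weeks runs from 1.9 to 22.5 points. The upper end is severe: 15% per 12 weeks is 1 - 0.85^3 = 39% per 36 weeks. If no responder has such an event, d = 0 and the gap is zero.

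**The case against.** The strongest reply is that the objective concerns reduction in fibrosis and the SAP defines it histologically. On that view death is simply outside the endpoint, and whether the curve is too high depends on an estimand that the documents never state. This stands in part. A reader might infer that the plan exaggerates durability outright, but the documents do not support so one-sided a reading: against the cumulative incidence of histological loss, the same curve is pessimistic. What survives is that the curve matches neither natural quantity.

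A reader might also infer that every responder who deteriorates leaves without a further biopsy. That is certain only for death. Much of IWG-MRT progression (protocol Appendix B) is spleen growth, which does not prevent a biopsy, and progression is not among the listed removal reasons in protocol 7.14. Appendix J does make continued extension dosing conditional on absence of progression. Transplant as an on-study event is not addressed at all. Because protocol 1.1 says that fibrosis resolves after successful transplant, a post-transplant biopsy could even lengthen a recorded response.

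Other outputs help only partly. Time to treatment failure is exploratory and not limited to responders. IWG-MRT categories by visit and deaths by arm are reported separately. The rule in SAP 4.9 that counts missing post-baseline response as non-response concerns response status and does not create an event in the duration curve. The earlier Stage 2 SAP cited in SAP section 1 was not available and may contain further rules.

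**Conclusion.** The concern holds in limited form. As written, the duration rule censors responders who die. Once competing events occur, the resulting curve estimates neither the proportion alive, event-free and in response nor, through its complement, the cumulative incidence of histological loss.

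Under the assumed rates the first error is about 3-8 points at 24 weeks and 5-14 points at 96 weeks. These sizes are not findings about this trial. The 15% is all-cause discontinuation among enrolled subjects, not death or progression among responders. Nor can the 96-week gap be judged against a standard error computed as if all 13 responders were followed to that time, because optional biopsies would leave far fewer at risk.

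In the main stage, with at most 24 weeks of observed duration and 11-13 responders per higher-dose arm, most censoring is probably administrative. The point bears mainly on the extension. It concerns a secondary endpoint for which the SAP plans a plot and names no median. The primary bone marrow response rate is unaffected. It is a worthwhile, low-cost improvement.

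**What to change.** In SAP 2.2.2 and 4.4.2:
- State the estimand for Stage 2 duration of marrow response.
- Count death and leukemic transformation as end of response, or as competing events, and not as censoring.
- Show a composite curve (histological loss, IWG-MRT progression, transplant or new anti-myelofibrosis therapy where recorded, or death) together with the cumulative incidence of histological loss. Including all progression and transplant is partly a choice of estimand, so these two belong side by side.
- Do not let biopsies taken after transplant extend a response.
- Report reasons for censoring by arm, and keep the histological-only curve as a supplement.
- Align the two sections on grades worse than baseline.

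The cost is SAP wording, reprogramming of the existing plot and one more plot. Durations will look somewhat shorter. Follow-up ends about four weeks after the last visit (SAP 4.7.2) or after withdrawal (protocol 8.6), so later deaths, transplants or therapies may be unrecorded. The present SAP post-dates the Stage 2 primary lock and analysis, so for main-stage data the change should be labelled as made after that analysis.

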It is underscored that the consensus definition of a CR bone marrow is to be used only in those patients in which all other criteria are met, including resolution of leukoerythroblastosis. It should also be noted that it was a particularly difficult task for the working group to reach a consensus regarding what represents a complete histologic remission.

‡Immature myeloid cells constitute blasts + promyelocytes + myelocytes + metamyelocytes + nucleated red blood cells. In splenectomized patients, <5% immature myeloid cells is allowed.

§See above for definitions of anemia response, spleen response, and progressive disease. Increase in severity of anemia constitutes the occurrence of new transfusion dependency or a  $\geq 20$  g/L decrease in hemoglobin level from pretreatment baseline that lasts for at least 12 weeks. Increase in severity of thrombocytopenia or neutropenia is defined as a 2-grade decline, from pretreatment baseline, in platelet count or absolute neutrophil count, according to the Common Terminology Criteria for Adverse Events (CTCAE) version 4.0. In addition, assignment to CI requires a minimum platelet count of  $\geq 25,000 \times 10^9/L$  and absolute neutrophil count of  $\geq 0.5 \times 10^9/L$ .

||Applicable only to patients with baseline hemoglobin of <100 g/L. In patients not meeting the strict criteria for transfusion dependency at the time of study enrollment (see as follows), but have received transfusions within the previous month, the pretransfusion hemoglobin level should be used as the baseline.

¶Transfusion dependency before study enrollment is defined as transfusions of at least 6 units of packed red blood cells (PRBC), in the 12 weeks prior to study enrollment, for a hemoglobin level of <85 g/L, in the absence of bleeding or treatment-induced anemia. In addition, the most recent transfusion episode must have occurred in the 28 days prior to study enrollment. Response in transfusion-dependent patients requires absence of any PRBC transfusions during any consecutive "rolling" 12-week interval during the treatment phase, capped by a hemoglobin level of  $\geq 85$  g/L.

#In splenectomized patients, palpable hepatomegaly is substituted with the same measurement strategy.

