- To assess IWG-MRT response (Complete Response, Partial Response, Clinical Improvement), stable and progressive disease in subjects treated with three doses of PRM-151

Exploratory Objectives

• To measure changes in bone marrow fibrosis by quantitative image analysis and evaluate changes in bone marrow morphology in subjects receiving PRM-151

- To assess the effect of PRM-151 on other disease related parameters, including hematologic abnormalities and spleen size
- To assess the effect of PRM-151 on prognostic factors associated with increased mortality as measured by the DIPSS (Dynamic International Prognostic Scoring System)
- To evaluate the interaction between selected genetic mutations and cytogenetic abnormalities and response to PRM-151
- To explore potential biomarkers of PRM-151 activity in bone marrow samples
- To assess the effect of PRM-151 on bone marrow metabolism by PET imaging (at selected institutions)
- To evaluate the correlation of baseline PTX-2 levels with outcomes
- To evaluate the relationship between bone marrow fibrosis reduction and hematologic improvements in subjects treated with PRM-151
- To measure progression-free and overall survival in subjects receiving PRM-151

Study Endpoints:

Primary:

• Bone marrow response rate, defined as the percent of subjects with a reduction in bone marrow fibrosis score by at least one grade according to WHO criteria (Appendix D) at any time during the study as determined by a central adjudication panel of expert hematopathologists, blinded to subject, treatment, and time of biopsy

Secondary:

- Comparison of primary and secondary efficacy parameters between doses
- Incidence of adverse events (AEs), serious adverse events (SAEs), and changes in laboratory test results
- Bone marrow improvement:
 - o Bone marrow response rate at weeks 12, 24, and 36
 - Duration of bone marrow response
- Hemoglobin improvement

Baseline Status	Categories of Hemoglobin Improvement
Subjects who are transfusion dependent (≥ 2	Percent of subjects with
units PRBC every 4 weeks for 12 weeks	Red cell transfusion independence (no
prior to or after C1D1), regardless of baseline	transfusions for ≥ 12 consecutive weeks)
hemoglobin level	
	OR
	50% reduction in RBC transfusions for ≥ 12
	consecutive weeks

Subjects with baseline hemoglobin < 100 g/L	Percent of subjects with ≥ 10 g/L and ≥ 20
AND	g/L increase in hemoglobin for ≥ 12
Not transfusion dependent	consecutive weeks without transfusions

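### SAP 2.2.2 adds an 80 g/L hemoglobin condition to both limbs of hemoglobin improvement in transfusion-dependent subjects; the protocol has none, and the SAP does not say which value must meet it.

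*SAP*

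**What the plan says.** Protocol 3.2, in the row for transfusion-dependent subjects, offers two routes to improvement: no red cell transfusions for at least 12 consecutive weeks, or "50% reduction in RBC transfusions for" at least that long. The outcome column sets no hemoglobin condition on either route. The protocol synopsis has the same table, and SAP Appendix 3 reprints it: "50% reduction in RBC transfusions for ≥ 12" consecutive weeks, again with no floor.

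SAP 2.2.2 (Stage 2, hemoglobin improvement) rewrites both routes. The first becomes "absence of any packed red blood cells (PRBC) transfusion during any consecutive 12 weeks interval with hemoglobin level of ≥80g/L". The second becomes "at least a 50% reduction in PRBC transfusions for 12 consecutive weeks with hemoglobin level of ≥80g/L". Dependence at baseline is "at least 2 units every 4 weeks for 12 weeks prior to Cycle [C]1Day [D]1".

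The only comparable rule in the protocol is the IWG-MRT anemia response in Appendix B. There, complete absence of transfusions over a rolling 12-week interval must be "capped by a hemoglobin level of" at least 85 g/L. That rule belongs to a different endpoint, covers full independence only, and uses the value that closes the interval.

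**The concern.** The SAP contains two definitions of one endpoint: its own Section 2.2.2 and the protocol text in its Appendix 3. They can classify the same subject differently. The halving limb is the more exposed of the two, because a subject who has halved transfusions will often still be receiving some, at a low hemoglobin. If a low value is one of those counted, the subject drops out of the numerator although transfusion need has fallen as the protocol requires. The result then depends partly on when local practice triggers a transfusion and on when the blood count was taken.

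The classification is used more than once. Protocol 10.6.1.3.4 plans pairwise dose comparisons on every categorical secondary endpoint. SAP 4.4.2 computes duration of improvement only in subjects who improve. SAP 4.8 repeats the secondary endpoints in the extension population, where applicable.

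**Working it through.** The documents give no sample size, power or expected rate for this endpoint, so there is no planned figure to reproduce. The check compares the texts, works one subject through both definitions, and then illustrates the possible loss.

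**1. Texts side by side**

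| Source | No-transfusion limb | 50%-reduction limb |
|---|---|---|
| Protocol 3.2 and synopsis | no hemoglobin condition | no hemoglobin condition |
| SAP Appendix 3 | no hemoglobin condition | no hemoglobin condition |
| SAP 2.2.2 | at least 80 g/L | at least 80 g/L |
| Protocol Appendix B (IWG-MRT anemia response) | at least 85 g/L, closing value | no such limb |

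The figure 80 g/L appears nowhere else in the documents. The parallel platelet limb in SAP 2.2.2, which also rewards a reduction of at least 50% in transfusion need, has no platelet count floor.

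**2. One subject**

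- Baseline at the SAP's own threshold: 2 units per 4 weeks × 3 four-week periods = 6 units per 12 weeks.
- On treatment: 3 units per 12 weeks. Reduction = (6 − 3)/6 = 50%.
- Protocol 3.2: responder.
- SAP 2.2.2: non-responder if a hemoglobin that counts is below 80 g/L, otherwise responder.

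**3. Illustrative size of the loss in the halving limb**

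Assumptions, none of them from the documents: hemoglobin falls linearly between transfusions, and each scheduled count falls at an independent random point of that decline. Let s be the share of time below 80 g/L and q = 1 − s.

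- Cycling 95 to 75 g/L: s = 5/20 = 0.25, q = 0.75.
- Cycling 90 to 70 g/L: s = 10/20 = 0.50, q = 0.50.
- Transfused at 80 g/L or above: s = 0, no loss.

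Counts are scheduled on Day 1 of each 28-day cycle (Protocol 8.4), so a 12-week window with both ends included holds four. Cycles 2 to 9 Day 1 plus Cycle 9 Day 29 give 8 + 1 = 9 counts after baseline.

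- Closing value only: loss = 1 − q.
- All four counts in one fixed window: loss = 1 − q⁴.
- Any run of four passing counts among nine, with the halving sustained for all 36 weeks: loss = 1 − q⁴[1 + 4(1 − q) + (1 − q)(1 − q⁴)].

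| Reading of the SAP condition | 95 to 75 g/L | 90 to 70 g/L |
|---|---|---|
| Closing value only | 25% | 50% |
| All four, one fixed window | 1 − 0.316 = 68% | 1 − 0.0625 = 94% |
| Any run of four among nine | 1 − 0.687 = 31% | 1 − 0.217 = 78% |

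For the same assumed subjects the loss moves between 25% and 68%, or between 50% and 94%, according to a timing rule that the SAP leaves unstated.

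**The case against.** A floor has a rationale. Without one, a site that simply transfuses later can produce a 50% reduction with no drug effect, so the protocol's limb also depends on practice. Appendix B shows that pairing a transfusion response with a hemoglobin level is an accepted idea. Whether a floor is desirable is therefore a legitimate design question, and this point does not settle it.

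A reader might infer that any subject transfused below 80 g/L automatically fails, so that the halving limb defeats itself. The SAP does not support that. It does not say which value counts; under a closing-value rule, or if only Day 1 counts are used, such a subject can still pass. Nor should the 68% to 94% figures be read as an estimate. They rest on assumed cycling ranges, independent sampling times and one fixed window, whereas the no-transfusion limb speaks of any 12-week interval and neither limb fixes a particular window. Visits every 28 days and roughly periodic transfusions also make independence doubtful.

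A reader might also take the protocol phrase "regardless of baseline hemoglobin level" as ruling out a floor. It stands in the baseline column and determines only who enters the row. The argument rests on the outcome column, which sets no hemoglobin condition.

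Other mitigating facts stand. SAP 2.2.3 separately reports units transfused in the prior 12 weeks, and their change to Week 36, in transfusion-dependent subjects with no floor. The endpoint is secondary, concerns a subset, and under Protocol 10.3.3 and 10.6.1.3.4 is compared without multiplicity adjustment and with stated caution. The earlier Stage 2 SAP (Version 2.0, 5 March 2018), signed before the Stage 2 primary lock, is not available here; the floor may have come from it with a reason. None of this removes the conflict between SAP 2.2.2 and the protocol text that the same SAP reprints.

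**Conclusion.** The SAP definition is wrong as written. It adds an unexplained condition to both limbs of a protocol-defined secondary endpoint, contradicts its own Appendix 3, and omits the timing needed to program the condition. The change can turn a protocol responder into a SAP non-responder, as the 6-to-3-unit subject shows. That conclusion needs no assumption beyond one counted hemoglobin below 80 g/L.

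The size is unknown. The illustrations run from 0% to 94% of true halvers, depending on trough levels and on the reading of the condition, and the documents supply neither. The consequence is confined to one secondary endpoint, its duration analysis and its repeat in the extension; no primary dose claim depends on it. It still matters because, per SAP Section 1, this SAP was written for the final analysis, after the Stage 2 primary lock. At that stage an undocumented change in who counts as a responder is hard to defend.

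**What to change.** In SAP 2.2.2, make the Protocol 3.2 definition the reported secondary endpoint for transfusion-dependent subjects, with no hemoglobin condition on either limb. This also brings the section into line with SAP Appendix 3.

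If the 80 g/L version is wanted, keep it as a labelled supplementary analysis. State which hemoglobin must meet the threshold (every value in the 12 weeks, pre-transfusion values, scheduled Day 1 values, or the closing value), give the reason, and record the change in the study report as Protocol 10.3.1 requires. The 85 g/L level in Appendix B should not be substituted, since it belongs to the IWG-MRT anemia response.

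The cost is a wording change and a simpler derivation, plus one extra table if the supplementary version is kept. Transfusion diaries and blood counts are already collected, so no new data are needed.
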